^g Pre-dose (within 60 minutes prior to start of infusion). For patients in the MEDI4736 + tremelimumab combination therapy arm: pre-dose samples for both MEDI4736 and tremelimumab can be taken within 60 minutes prior to the start of the tremelimumab infusion.

^h Within 10 minutes of the end of infusion.

ⁱ If screening assessments are performed within 3 days prior to Day 1 (first infusion day), they do not need to be repeated at Day 1.

^j Free T₃ or free T₄ will only be measured if TSH is abnormal or if there is clinical suspicion of an AE related to the endocrine system.

^k For women of childbearing potential only. A pregnancy test must be performed within 7 days before Cycle 1 Day 1. A urine or serum pregnancy test is acceptable.

^l Results for electrolytes, full blood count, and liver function tests must be available before commencing an infusion (within 3 days).

^m During the combination portion of treatment, tremelimumab will be administered first; the MEDI4736 infusion will start approximately 1 hour (maximum 2 hours) after the end of the tremelimumab infusion. If there are no clinically significant infusion reactions with the first cycle, then for all other cycles, MEDI4736 can be given immediately after the tremelimumab infusion has finished.

ⁿ Patients will complete PROs using handheld devices at home.

^o CCI

^p MEDI4736 + tremelimumab combination therapy only: The collection of tumor biopsies at the time of progression prior to retreatment is mandated; the Investigator must consult with the Study Physician if such sampling is not feasible.

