Patient-reported outcome assessments^o									
EORTC QLQ-C30, CCI	X	X						q8w (±3 days) relative to the date of Cycle 1 Day 1	
EORTC QLQ-H&N35, CCI	X	X						q4w (±3 days) relative to the date of Cycle 1 Day 1	
Other laboratory assessments and assays									
Tumor biopsy or obtain archival tumor tissue <3 years old for PD-L1 status	X ^c								
Tumor evaluation (CT or MRI) (RECIST 1.1) ^q	X	First on-treatment scan at 6 weeks (+1 week) and then q6w (±1 week) for the first 24 weeks relative to the date of randomization and then q8w (±1 week) thereafter							

CCI

Window for visits is relative to day of dosing, even if dosing is delayed, unless otherwise specified.

- ^a Cycle 1 Day 1 procedures do not need to be repeated if the same procedures were performed for screening purposes 3 days prior to Cycle 1 Day 1.
- ^b Patient visits will change from q3w to q4w after completion of chemotherapy.
- ^c Informed consent of study procedures and tumor sample acquisition may be obtained prior to the 28-day screening window, if necessary, in order to permit tumor sample acquisition and analysis prior to randomization. PD-L1 testing will be done from a newly acquired tumor biopsy (preferred) or archival tissue (<3 years old).
- ^d Pre-dose and as clinically indicated before every infusion or administration.
- ^e Any clinically significant abnormality detected requires a confirmatory ECG.
- ^f HPV status testing may be performed for oropharyngeal tumors only. Local testing is acceptable and preferred. If HPV status is unknown or unavailable locally, a newly acquired or archived tumor sample must be submitted for central testing at a reference laboratory as described in the Laboratory Manual.
- ^g To be collected q3w prior to the start of infusion and as clinically indicated. Electrolytes should be monitored with cetuximab therapy as per institution guidelines.

- h If screening assessments are performed within 3 days prior to Day 1 (first infusion day), they do not need to be repeated at Day 1.
- i If the patient does not complete treatment through Cycle 5, TSH should be obtained after the patient's last cycle.
- j Free T₃ or free T₄ will only be measured if TSH is abnormal or if there is clinical suspicion of an AE related to the endocrine system.
- k For women of childbearing potential only. A pregnancy test must be performed within 7 days before Cycle 1 Day 1. A urine or serum pregnancy test is acceptable.

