Chloride ^b	Total protein
Creatinine clearance ^b	Urea or blood urea nitrogen, depending on local practice
Creatinine	
Gamma glutamyltransferase ^b	

^a Tests for ALT, AST, alkaline phosphatase, and total bilirubin must be conducted and assessed concurrently. If total bilirubin is $\geq 2 \times$ upper limit of normal (and evidence of Gilbert's syndrome) then fractionate into direct and indirect bilirubin.

^b Bicarbonate (where available), chloride, creatinine clearance, gamma glutamyltransferase, and magnesium testing are to be performed at screening, on Day 1 (unless screening laboratory assessments are performed within 3 days prior to Day 1), and if clinically indicated.

^c For patients receiving cetuximab, magnesium monitoring and subsequent supplementation may occur more frequently as clinically indicated per site specific standards.

ALT Alanine aminotransferase; AST Aspartate aminotransferase

Table 6 Hematology

Eosinophils	Neutrophils
Hematocrit	Partial thromboplastin time
Hemoglobin	Platelet count
International normalized ratio	Red blood cell count
Lymphocytes	Total white cell count
Monocytes	

Note: For coagulation parameters, activated partial thromboplastin time and international normalized ratio are to be assessed at baseline and as clinically indicated.

Table 7 **Urinalysis^a**

Bilirubin	Ketones
Blood	pH
Color and appearance	Protein
Glucose	Specific gravity

^a Urinalysis must be done at baseline and then as clinically indicated.

Note: Microscopy should be used as appropriate to investigate white blood cells and use the high power field for red blood cells.

If a patient shows an AST or ALT $\geq 3 \times$ ULN together with total bilirubin $\geq 2 \times$ ULN, refer to [Appendix D](#) for further instructions. These cases should be reported as SAEs if, after evaluation, they meet the criteria for a Hy's Law case or if any of the individual liver test parameters fulfill any of the SAE criteria. All patients with an elevated AST, ALT, or bilirubin value (the latter at $\geq 1.5 \times$ ULN) at the time of the last dose of study treatment should have a further liver chemistry profile (AST, ALT, bilirubin, and alkaline phosphatase) performed 30 days (± 3 days) after permanent discontinuation of study treatment.

Any clinically significant abnormal laboratory values should be repeated as clinically indicated and recorded on the eCRF. Situations in which laboratory safety results should be reported as AEs are described in Section [6.3.4](#).

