### 3.3.4 Laboratory data

Laboratory data will be collected throughout the study, from screening to the follow-up visits as described in Tables 2, 3 and 4 of the CSP. Blood and urine samples for determination of hematology, clinical chemistry, and urinalysis will be collected as described in Section 5.2.1

of the CSP. For derivation of baseline and post baseline visit values considering visit window and how to handle multiple records, derivation rules as described in Section 3.3.7 below will be used.

Change from baseline in hematology and clinical chemistry variables will be calculated for each post-dose visit on treatment. CTCAE grades will be defined at each visit according to the CTCAE grade criteria using local or project ranges as required, after conversion of lab result to corresponding SI units. The following parameters have CTCAE grades defined for both high and low values: Potassium, Sodium, Magnesium, Glucose and Corrected calcium so high and low CTCAE grades will be calculated.

Corrected Calcium will be derived during creation of the reporting database using the following formula:

$$\text{Corrected calcium (mmol/L)} = \text{Total calcium (mmol/L)} + ([40 - \text{Albumin (G/L)}] \times 0.02)$$

Absolute values will be compared to the project reference range and classified as low (below range), normal (within range or on limits of range) and high (above range).

The maximum or minimum on treatment value (depending on the direction of an adverse effect) will be defined for each laboratory parameter as the maximum (or minimum) post-dose value at any time.

Local reference ranges will be used for the primary interpretation of laboratory data. The denominator used in laboratory summaries of CTCAE grades will only include evaluable patients, in other words those who had sufficient data to have the possibility of an abnormality.

For example:

- If a CTCAE criterion involves a change from baseline, evaluable patients would have both a pre-dose and at least 1 post-dose value recorded.
- If a CTCAE criterion does not consider changes from baseline, to be evaluable the patient needs only to have 1 post dose-value recorded.

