- Baseline will be defined as the last non-missing measurement prior to dosing with study treatment. For the re-treatment period then baseline is similarly defined as the last non-missing measurement prior to the first dose on the re-treatment period. For laboratory data, any assessments made on day 1 will be considered pre-dose. Alternatively, if two visits are equally eligible to assess patient status at baseline (e.g., screening and baseline assessments both on the same date prior to first dose with no washout or other intervention in the screening period), the average can be taken as a baseline value. For non-numeric laboratory tests (i.e., some of the urinalysis parameters) where taking an average is not possible then the best value would be taken as baseline as this is the most conservative. In the scenario where there are two assessments on day 1, one with time recorded and the other without time recorded, the one with time recorded would be selected as baseline. Where safety data are summarized over time, study day will be calculated in relation to date of first study treatment.

Missing safety data will generally not be imputed. However, safety assessment values of the form of “ $< x$ ” (i.e., below the lower limit of quantification) or “ $> x$ ” (i.e., above the upper limit of quantification) will be imputed as “ $x$ ” in the calculation of summary statistics but displayed as “ $< x$ ” or “ $> x$ ” in the listings. Furthermore:-

- For missing diagnostic dates, if day and/or month are missing use 01 and/or Jan. If year is missing, put the complete date to missing.
- For missing start AE dates, the following will be applied
  1. Missing day- Impute the 1st of the month unless month is the same as month of the first dose of study drug then impute first dose date
  2. Missing day and month -Impute 1st January unless year is the same as first dose date then impute first dose date
  3. Completely missing-impute first dose date unless the end date suggests it could have started prior to this in which case impute the 1st January of the same year as the end date
- For missing end AE dates, the following will be applied:
  - Missing day - Impute the last day of the month unless month is the same as month of the last dose of study drug then impute last dose date.

- Missing day and month – impute 31st December unless year is the same as last dose date then impute last dose date.

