#### **4.2.13.2 Laboratory assessments**

Data obtained up until the 90 days following discontinuation of IP or until the initiation of the first subsequent therapy following discontinuation of IP (whichever occurs first) will be used for reporting. This will more accurately depict laboratory toxicities attributable to IP only as a number of toxicities up to 90 days following discontinuation of IP are likely to be attributable to subsequent therapy.

Data summaries and listings will be provided in International System (SI) of units.

All laboratory data will be listed. Flags will be applied to values falling outside - reference ranges (which will be explicitly noted on these listings where applicable), and to values for which CTCAE grading applies.

Scatter plots (shift plots) of baseline to maximum/minimum value (as appropriate) on treatment (i.e. on treatment is defined as data collected between the start of treatment and the relevant follow-up period following the last dose of IP) may be produced for certain parameters if warranted after data review.

Boxplots of absolute values by week, and boxplots of change from baseline by week, may be presented for certain parameters if warranted after data review up to Week 40.

Shift tables for laboratory values by worst common toxicity criteria (CTCAE) grade will be produced, and for specific parameters separate shift tables indicating hyper- and hypo-directionality of change will be produced. The laboratory parameters for which CTCAE grade shift outputs will be produced are:

- Hematology: Hemoglobin, Leukocytes, Lymphocytes, absolute count, Neutrophils, absolute count, Platelets
- Clinical chemistry: ALT, AST, Alkaline Phosphatase (ALP), Total bilirubin, Albumin, Magnesium – hypo and – hyper, Sodium – hypo and – hyper, Potassium – hypo and – hyper, Corrected calcium – hypo and – hyper, Glucose – hypo and – hyper, GGT, Creatinine

For the parameters with no CTCAE grading that are listed in the CSP, shift tables from baseline to worst value on treatment will be provided. Additional summaries will include a

shift table for urinalysis (Bilirubin, Blood, Glucose, Ketones, Protein) comparing baseline value to maximum on treatment value.

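### Magnesium and GGT have no explicitly scheduled test after Day 1, but their CTCAE percentages count only patients with a post-dose value, so the rates are probably inflated and, for magnesium, may not be comparable between arms

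*SAP*

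**What the plan says.** **Testing schedule.** Protocol Tables 2, 3 and 4 mark clinical chemistry at each treatment cycle and at the early follow-up visits. Table 5 (Section 5.2.1) then takes five analytes out of that routine. Footnote b says "gamma glutamyltransferase, and magnesium testing are to be performed at screening, on Day 1" and, after that, only where there is a clinical reason. The other three analytes are bicarbonate, chloride and creatinine clearance. Footnote c adds: "For patients receiving cetuximab, magnesium monitoring and subsequent supplementation may occur more frequently as clinically indicated per site specific standards". Table 3 footnote g, for the SoC arm, says "Electrolytes should be monitored with cetuximab therapy as per institution guidelines". For urinalysis, the Table 7 footnote says "Urinalysis must be done at baseline and then as clinically indicated".

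**Status of Day 1.** SAP 3.3.7: "For laboratory data, any assessments made on day 1 will be considered pre-dose".

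**Denominator.** SAP 3.3.4: "The denominator used in laboratory summaries of CTCAE grades will only include evaluable patients". A patient is evaluable with one post-dose value, plus a pre-dose value where the CTCAE criterion uses change from baseline. Protocol 8.4.2.2 has a similar sentence covering laboratory summaries in general.

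**Outputs.** SAP 4.2.13.2 lists the parameters with CTCAE shift outputs, beginning "Clinical chemistry: ALT, AST, Alkaline Phosphatase (ALP), Total bilirubin, Albumin, Magnesium" (low and high directions). GGT appears later in the same list. Urinalysis gets a separate shift table from baseline to the maximum on-treatment value, without CTCAE grades.

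**The concern.** A tested-only denominator is reasonable when everyone is due to be tested at every cycle, because few patients drop out of it and those who do are not selected on the result. It behaves differently when the test is done for cause. The denominator is then made up largely of patients in whom a clinician suspected something, and the percentage abnormal among them is not an estimate of the rate in treated patients.

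This matters because the safety objective (Protocol 2.3) is comparative against SoC and names laboratory findings as an outcome. Protocol 6.3.4 also keeps most deteriorations in protocol-mandated laboratory values out of AE reporting unless they are serious, lead to discontinuation or come with signs or symptoms. For such values, the laboratory tables are the main record of non-serious abnormalities. Nothing in SAP 3.3.4 or 4.2.13.2 asks for the number tested to be displayed as a share of treated patients, or for for-cause rows to be marked.

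**Working it through.** The documents state no abnormality rate or testing rate for these analytes, so there is no planned figure to reproduce. The check has two parts.

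**1. Does the plan leave any scheduled post-dose value?**

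- Scheduled magnesium and GGT tests: screening and Day 1 (Table 5 footnote b).
- Screening precedes dosing, and Day 1 is pre-dose by SAP 3.3.7.
- Explicitly scheduled post-dose values under footnote b: none.
- Entry to the CTCAE denominator therefore depends on an unscheduled test, subject to the open question on Table 2 footnote l discussed under the objection.
- Both analytes are in the CTCAE shift list, so the denominator rule applies to both. Urinalysis, chloride, bicarbonate and creatinine clearance are not in that list.

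**2. How far could the percentage move?** All inputs here are assumptions. Let p be the true proportion abnormal, s1 the probability of a post-dose test in an abnormal patient, and s0 the same probability in a patient who is not abnormal.

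- Proportion tested: t = p·s1 + (1 − p)·s0
- Percentage among tested: p·s1 / t
- Percentage over all treated: p·s1
- Ratio of the tested-only rate to the true rate: s1 / t

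Example: p = 0.10, s1 = 0.6, s0 = 0.1. Then t = 0.06 + 0.09 = 0.15, the tested-only rate is 0.06/0.15 = 40.0%, and the all-treated rate is 6.0%.

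For p = 10% in an arm of 190 (the planned size of the monotherapy and SoC arms, used only to scale the counts):

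| s1 / s0 | Tested (about) | Among tested | Over all treated | Ratio to truth, tested-only |
|---|---|---|---|---|
| 1 / 1 | 190 | 10.0% | 10.0% | 1.00 |
| 0.3 / 0.3 | 57 | 10.0% | 3.0% | 1.00 |
| 0.8 / 0.5 | 101 | 15.1% | 8.0% | 1.51 |
| 0.6 / 0.3 | 63 | 18.2% | 6.0% | 1.82 |
| 0.6 / 0.1 | 29 | 40.0% | 6.0% | 4.00 |

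For the three selective patterns, the ratio is 1.55, 1.90 and 4.80 when p = 5%, and 1.43, 1.67 and 3.00 when p = 20%. Across p from 5% to 20%, the tested-only rate is thus about 1.4 to 4.8 times the true rate when abnormal patients are likelier to be tested, and 1.0 times when testing is unrelated to abnormality.

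**Between arms.** Take two arms with the same true rate of 10%, one tested at 0.6/0.1 and the other at 0.8/0.5. The tested-only table shows 40.0% against 15.1%; the all-treated table shows 6.0% against 8.0%. Neither contrast is real, and they point in opposite directions. Unequal testing therefore cannot be repaired by choosing one denominator over the other.

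**The case against.** **The tests may in fact be done every cycle.** Table 2 footnote l says "Results for electrolytes, full blood count, and liver function tests must be available before commencing an infusion (within 3 days"). If sites read electrolytes to include magnesium, and liver function tests to include GGT, most immunotherapy patients would have post-dose values and the selection largely disappears. This stands as an open question. Footnote l names neither analyte, footnote b removes both from per-cycle testing, and the liver chemistry profile spelled out in Section 5.2.1 (AST, ALT, bilirubin, alkaline phosphatase) omits GGT. Sites could differ, which is itself a reason to show the number tested.

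**Routine testing in the SoC arm is not established.** This also stands. Footnote c permits more frequent magnesium monitoring but ties it to clinical need and site standards. Table 3 footnote g sets no frequency and does not name magnesium. A reader might infer that the SoC percentage is close to a true rate while the other two arms are distorted; the documents support only a possible difference in monitoring.

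**The arm difference is confined to magnesium.** A reader might extend it to GGT or urinalysis. Footnote b treats GGT alike in all arms, and the Table 7 footnote makes no arm distinction.

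**The CTCAE rule does not reach urinalysis, chloride, bicarbonate or creatinine clearance.** Correct: none is in the CTCAE shift list. Only the broader sentence in Protocol 8.4.2.2 could cover them. The urinalysis shift table still rests on for-cause samples, so a label there is useful.

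**The impact is limited.** SAP 4.2.13 plans no formal safety analysis, counts are shown beside percentages, and symptomatic cases reach the AE tables. Protocol 6.3.4 also asks for clinically relevant deteriorations in non-mandated parameters to be reported as AEs, and a site might treat a for-cause magnesium result that way. All of this lowers the stakes. It does not remove the problem, because a count without the number tested and treated cannot tell a reader how selective the testing was.

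**Conclusion.** The point holds for magnesium and GGT. As written, the plan produces CTCAE percentages among patients with an unscheduled post-dose test, and those percentages are likely to exceed the true rates. The direction rests on one assumption, that patients tested for cause are more often abnormal than those not tested. If they are not, there is no inflation. The size cannot be derived from the documents; the factor of about 1.4 to 4.8 is illustrative and depends on assumed testing probabilities.

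For magnesium, the arms may also not be comparable, because the protocol allows closer monitoring with cetuximab. For GGT, the selection is the same in all arms and no documented schedule difference separates them. A reader might conclude that the magnesium contrast will be reversed, or that rates are certainly inflated in the immunotherapy arms alone; neither follows, since no testing rate is given for any arm and footnote l leaves the immunotherapy schedule unclear. The consequence is limited to descriptive safety tables.

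**What to change.** In SAP 3.3.4 and 4.2.13.2, for magnesium and GGT:

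- show by arm the number and percentage of treated patients with at least one post-dose test;
- report abnormalities over tested patients and over all treated patients, labelling the latter as a lower bound;
- footnote the rows as for-cause testing not suited to between-arm comparison.

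Add the number tested and the same footnote to the urinalysis shift table. Keep the evaluable-only denominator for analytes scheduled at every cycle.

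Reconcile Table 2 footnote l with Table 5 footnote b, so that it is clear whether magnesium and GGT belong to the pre-infusion tests. If they do, the for-cause footnote would need revising for the immunotherapy arms.

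The cost is SAP wording, table shells and slightly larger tables; no new data are needed. The downside is that the all-treated percentage understates the true rate whenever some abnormal patients go untested, and does so more in an arm that detects a smaller share of them. It should therefore stand beside the tested-only figure and not replace it.

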### **3.3.5 ECGs**

ECG data obtained up until 90 days after date of last dose of study treatment, or until initiation of another therapy, will be used for reporting. For derivation of post baseline visit values considering visit window and to handle multiple records present in any visit window, derivation rules as described in Section 3.3.7 below will be used.

Investigator's assessment of the ECG will be collected locally.

### **3.3.6 Vital signs**

Vital signs (blood pressure [BP], pulse, respiratory rate, and temperature) will be evaluated according to the assessment schedules (Tables 2, 3, and 4 from CSP).

Vital signs data obtained up until 90 days after date of last dose of study treatment, or until initiation of another therapy, will be used for reporting. Change from baseline in vital signs variables will be calculated for each post-dose visit on treatment. For derivation of post baseline visit values considering visit window and to handle multiple records, derivation rules as described in Section 3.3.7 below will be used.

The denominator in vital signs data should include only those patients with recorded data.

